11. STUDY MANAGEMENT AND ADMINISTRATION

11.1 ETHICAL CONDUCT OF STUDY (GCP)

The guidelines of the World Medical Association Declaration of Helsinki in its revised edition (48th General Assembly, Somerset West, Republic of South Africa, October 1996), the guidelines of ICH GCP (CPMP/ICH/135/95), as well as the demands of national drug and data protection laws and other applicable regulatory requirements, will be strictly followed. Approval will be obtained from the appropriate regulatory authorities before sites are initiated.

11.2 IRB AND ETHICS COMMITTEE APPROVAL

Prior to initiation of the study, the protocol, the informed consent form, the subject information sheet(s), details of the subject recruitment procedures and any other relevant study documentation will be submitted to the responsible IRB or Ethics Committee (EC). The Investigator will report promptly to the IRB/EC any new information that may adversely affect the safety of subjects or the conduct of the study. Similarly, the Investigator will submit written summaries of the study status to the IRB/EC annually, or more frequently if requested by the IRB/EC. Upon completion of the study, the Investigator will provide the IRB/EC with a brief report of the outcome of the study, if required.

11.3 PROTOCOL MODIFICATIONS

Modifications of the signed protocol are only possible by approved protocol amendments and with the agreement of all responsible persons. The procedure for approval of a protocol amendment is identical to that for approval of the protocol. The IRB/EC must be informed of all protocol amendments and should be asked for its opinion as to whether a full re-evaluation of the ethical aspects of the study is necessary by the committee. This should be fully documented. The Investigator must not implement any deviation from or change to the protocol, without discussion with, and agreement by, the study Sponsor and prior review and documented approval/favorable opinion of the amendment from the relevant IRB/EC, except where it is necessary to eliminate an immediate hazard to study subjects, or where the change(s) involves only logistical or administrative aspects of the study (e.g., change in CRA(s), change of telephone number(s)). Protocol amendments will be submitted to the appropriate authority(ies) as required by the applicable regulatory requirement(s).

11.4 SUBJECT INFORMATION AND CONSENT

The Investigator is responsible for ensuring that no subject will receive any study-related examination or activity before that subject has given an IRB/EC approved informed consent. The subject must give written consent after the receipt of detailed information. The verbal explanation will cover all the elements specified in the written information provided for the subject. The Investigator will inform the subject of the aims, methods, anticipated benefits and potential hazards of the study, including any discomfort it may entail. The subject must be given every opportunity to clarify any points he/she does not understand and if necessary, ask for more information. At the end of the interview, the subject may be given time to reflect if this is required, or if the subject requests more time. Subjects and/or legal guardian forms will be kept and archived by the Investigator in the Investigator's study file. It should be emphasized that the subject is at liberty to withdraw their consent to participate at any time, without penalty or loss of

benefits to which the subject is otherwise entitled. Subjects who refuse to give, or withdraw, written informed consent may not be included or continued in this study, but this will not impact their subsequent care. The Investigator will notify in writing each subject's primary care physician (or equivalent) of the subject's intent to participate in the study.

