5.2 DISCONTINUATION OF THERAPY

Study therapy MUST immediately be discontinued for any the following reasons:

- Radiographic evidence of tumor progression as defined by the Immune Related Response Criteria (see section 7.5)
- Withdrawal of informed consent (subject's decision to withdraw for any reason)
- Any clinical adverse event, laboratory abnormality, inter-current illness, or progression of disease which, in the opinion of the Principal Investigator, indicates that continued participation in the study is not in the best interest of the subject
- Pregnancy
- Termination of the study by the sponsor
- Imprisonment or the compulsory detention for treatment of either a psychiatric or physical (e.g., infectious disease) illness
- Subjects will also be discontinued based on 5.1a.

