Cycle 6+/- Follow up visits will occur every 14 days (+/- 2 days) for all subjects who remain on trial:

- Physical Exam
- Weight

- Vital Signs (pre-infusion)
- ECOG Evaluation
- Hematology panel: CBC with differential, platelets (pre-infusion)
- Chemistry panel and serum pregnancy (pre-infusion same tube). Serum pregnancy to be completed every 2 cycles.
- Urinalysis (pre-infusion)
- CRP (pre-infusion)
- PK Sampling (pre-infusion)
- Study Drug infusion
- Vital signs (60 minutes post-infusion)
- PK Sampling (30-90 minutes post-infusion)
- Adverse Event monitoring
- Concomitant Medications
- Tumor Measurements (every 8 weeks, i.e. within 7 days prior to C9D1, C13D1 etc.). Upon documentation of radiographic progression, confirmatory tumor measurements to be repeated at 4 weeks +/- 3 days only for patients who elect to continue on therapy until confirmation of progression. If this scan confirms progression, treatment is to be discontinued. If the confirmatory measurements indicate stable disease or better, the patient may elect to continue treatment with radiographic tumor assessments every 8 weeks from Day 1 of the current treatment cycle until progression.

End of Study Visit- This visit should be completed within 14 days for any subject who elects to come off trial or who comes off due to AEs, toxicities, or decline in performance status:

- Physical Exam
- Weight
- Vital Signs
- ECOG Evaluation
- Hematology panel: CBC with differential, platelets
- Chemistry panel
- Urinalysis
- CRP
- Adverse Event monitoring
- Serum Pregnancy
- PK Sampling
- EORTC QLQ-C30
- Concomitant Medications / Non-Drug Therapies review
- DEXA Scan--for any subject who completes visits at least through C3D1, but discontinues prior to C5D1
- Tumor Measurements--for subjects with clinical progression, every effort should be made to obtain radiographic restaging. If subjects are discontinued due to evidence of progressive disease, then tumor measurements do not need to be repeated.

Follow up for Overall Survival

Subjects, who come off trial for any reason after C1D1, will be contacted by phone after 30 days of the last dosing visit for adverse events and ECOG performance status, and at every 4-6 weeks

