there after to assess ECOG performance status. Patients will be considered lost to follow up after 3 documented consecutive unsuccessful contact attempts. Prior to any interim analysis, and once the trial has been completed, any subjects who have been lost to follow up will be queried against the Social Security Administration's Death Master File to determine date of death.

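### Deaths of patients who withdraw consent, or who are randomised but never dosed, can be missed in the ITT overall survival analysis, because the consent, follow-up, search and censoring rules do not fit together

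*Protocol*

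**What the plan says.** - **Protocol 11.4** (Subject Information and Consent): "Subjects who refuse to give, or withdraw, written informed consent may not be included or continued in this study". Survival follow-up is not mentioned.
- **Protocol 5.2** (Discontinuation of Therapy) lists, among reasons to stop study therapy, "Withdrawal of informed consent (subject's decision to withdraw for any reason".
- **Protocol 5.4**, on survival follow-up by phone: "Subjects, who come off trial for any reason after C1D1, will be contacted by phone after 30 days of the last dosing visit", and every 4 to 6 weeks after that.
- **Protocol 5.4**, definition of loss: "Patients will be considered lost to follow up after 3 documented consecutive unsuccessful contact attempts".
- **Protocol 5.4**, record search before each interim analysis and at trial completion: "any subjects who have been lost to follow up will be queried against the Social Security Administration's Death Master File".
- **Protocol 10.3** and **SAP 5.1** follow all subjects to death, loss to follow-up or study termination. Withdrawal of consent is not listed as an end of follow-up.
- **Protocol 10.4** censors patients who are lost or discontinued at their last contact.
- **SAP 3.1 and 8.4.1** give censoring rules for patients alive at the cutoff and for patients lost and untraceable. They have no rule for withdrawn consent.
- **SAP 7.1** defines ITT as all randomised patients. The SAP disposition shell counts loss to follow-up and withdrawal of consent as separate reasons.

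**The concern.** Overall survival in all randomised patients is the primary endpoint, so vital status is needed for each of them whatever happened to study treatment. The rules leave two groups uncovered.

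The first is patients who withdraw consent. A site that follows 11.4 literally makes no more calls. With no calls there can be no three failed attempts, so the patient never counts as lost and the record search never includes them. Protocol 10.4 then censors them at last contact. A site that follows 5.4 or 10.3 does the opposite, so ascertainment may differ between sites.

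The second is patients randomised but not dosed. The 5.4 phone rule starts after C1D1, which may be up to 7 days after randomisation. These patients are in the ITT set, but no contact schedule is written for them.

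Two things are at stake. Events are lost, which costs power. If patients withdraw because they are getting worse, and do so at different rates in the two arms, the hazard ratio is also biased.

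**Working it through.** **1. Following one patient through the rules**

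| Step | Patient withdraws consent, site applies 11.4 | Patient randomised, never dosed |
|---|---|---|
| Phone contact (5.4) | stopped by 11.4 | outside the rule (starts after C1D1) |
| Counts as lost (5.4) | no, because no attempts are made | only if someone attempts contact |
| Death-record search (5.4) | not covered | not covered unless lost |
| Censoring (10.4) | last contact | last contact, if treated as discontinued |

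**2. The plan's own event number**

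Inputs from SAP 5 and 5.1: HR 0.767 (medians 4.6 and 6.0 months), one-sided alpha 0.025, power 80%, 2:1 allocation, looks at 276, 414 and 552 deaths, efficacy cut-offs 0.0029, 0.0121 and 0.025, futility cut-offs 0.25 and 0.08.

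- Fixed design (Schoenfeld): (1.960 + 0.842)² / [(2/9) × (ln 0.767)²] = 7.85 / 0.01564 ≈ 502 deaths.
- Three-look design with those cut-offs, simulated at 552 deaths: power about 79.6%. The plan's 552 is reproduced.

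**3. Deaths expected at 18 months with no withdrawal**

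Assuming exponential survival and 18 months of follow-up for every patient:

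- Placebo: 200 × [1 − exp(−ln 2 × 18/4.6)] = 200 × 0.934 = 186.7
- MABp1: 400 × [1 − exp(−ln 2 × 18/6.0)] = 400 × 0.875 = 350.0
- Total ≈ 537

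**4. Deaths lost to untraced withdrawal**

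The documents give no withdrawal rate or timing. Assume a fraction w in each arm is censored at 2 months. Deaths by 2 months are 200 × 0.260 + 400 × 0.206 ≈ 134.6. Expected deaths = (1 − w) × 536.7 + w × 134.6.

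| w (assumed) | Expected deaths | Lost | Three-look power at HR 0.767 |
|---|---|---|---|
| 0% | 537 | 0 | 78.6% |
| 5% | 517 | 20 | 77.1% |
| 10% | 497 | 40 | 75.4% |
| 15% | 476 | 60 | 73.8% |

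The looks are rescaled to the reduced total in each row. The loss is about 1.5, 3.2 and 4.8 points.

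**5. Bias**

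True HR 0.767, with withdrawal assumed to fall uniformly 0 to 2 months before death and never traced (simulation):

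| MABp1 / placebo withdrawal (assumed) | Expected HR |
|---|---|
| 5% / 5% or 8% / 8% | about 0.76 to 0.77 |
| 4% / 8% | about 0.79 |
| 8% / 4% | about 0.74 |

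True HR 1, 18-month follow-up, withdrawal assumed at 70% of each withdrawn patient's survival time, single log-rank test at one-sided 0.025:

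| MABp1 / placebo withdrawal (assumed) | Type I error | Mean HR |
|---|---|---|
| 0% / 0% | about 2.8% | 1.00 |
| 5% / 5% | about 2.2% | 1.00 |
| 10% / 10% | about 2.8% | 1.00 |
| 10% / 5% | about 6.8% | 0.96 |
| 5% / 10% | about 1.2% | 1.03 |

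These rest on 3,000 simulated trials each, so the first three rows differ by little more than simulation noise. Equal withdrawal does no visible harm to the HR or to type I error. Unequal informative withdrawal does, in either direction.

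**The case against.** The strongest reply is that the plan already means to follow everyone. The phone rule in 5.4 covers any reason for coming off trial, the study calendar has a survival follow-up column after the end-of-study visit, and 10.3 does not end follow-up at withdrawal. The SAP censors early only patients who are lost and untraceable, which presumes that tracing was attempted. This stands: a patient who merely stops infusions has a written route into survival follow-up.

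A reader might infer from the gloss in 5.2, "decision to withdraw for any reason", that a patient who declines more infusions must be recorded as withdrawing consent and is then dropped under 11.4. The documents do not support that. Section 5.2 lists reasons to stop therapy and is not a coding rule, and the disposition shell offers other categories.

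A reader might also infer a power loss of about 10 points, since power at HR 0.79 is about 70%. That needs twice the withdrawal rate on placebo in a double-blind trial, all of it shortly before death and none of it traced. The documents give no reason to expect that.

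Finally, the consent form was not available for review, and 11.5 requires the investigator to obtain the authorisations needed to collect and use protected data. Permission for vital-status follow-up after withdrawal may therefore exist. Even so, 11.4 would still conflict with 5.4 and 10.3, the search would still name only the lost, and 10.4 would still censor the discontinued at last contact.

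**Conclusion.** The concern holds as a gap between sections. The protocol does not say what happens to survival follow-up when consent is withdrawn, its record search cannot reach a withdrawn patient who is no longer called, and its phone schedule omits patients who were randomised but never dosed.

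Under assumed untraced withdrawal of 5% to 15% at about 2 months, the cost is about 20 to 60 deaths and 1.5 to 5 points of power. Bias in the HR is possible but conditional: it needs withdrawal that is both informative and different between arms, and its direction cannot be predicted from the documents.

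A reader might also attribute the shortfall of 537 expected deaths against 552 required to this gap. It exists with no withdrawal at all and is a separate issue.

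The case for acting is that the remedy is cheap and protects the primary endpoint. It does not rest on a demonstrated large bias.

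**What to change.** 1. Reconcile Protocol 5.2, 5.4, 10.4 and 11.4 so that stopping study drug does not end survival follow-up, and so that withdrawal from treatment is recorded separately from withdrawal of consent to follow-up.
2. In 11.4, and in the consent form if it does not already do so, ask a withdrawing patient whether vital status may still be obtained by phone or from records, and record the answer.
3. In 5.4, extend the search before each analysis from the lost to every randomised patient without a known death date, where permitted. This includes patients who withdrew and patients never dosed. Start the contact schedule from randomisation.
4. In Protocol 10.4 and SAP 3.1 and 8.4.1, censor for OS at the last date known alive only when vital status cannot be obtained, and state that this covers withdrawn consent.

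The cost is protocol, SAP and possibly consent wording, plus a longer list for a search that is already planned. Some patients will refuse and will remain censored.

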11.5 DATA PROTECTION AND CONFIDENTIALITY

In signing the final protocol, every participating Investigator agrees to keep all information and results concerning the study and the investigational product confidential. The confidentiality obligation applies to all personnel involved at the investigational site. The Investigator must ensure that each participant's anonymity will be maintained in accordance with applicable laws. On eCRFs or other documents submitted to the Sponsor, subjects should not be identified by their name, but by subject ID number. The Investigator should keep a separate log of ID numbers, names and addresses. Documents that contain the names associated with these ID numbers (e.g. written consent/assent forms), are not for submission to the Sponsor and should be maintained by the Investigator in strict confidence except to the extent necessary to allow auditing by regulatory authorities, auditing or monitoring by the Institutional Review Board/EC, the Sponsor personnel or their affiliates and designees (such as CRAs).

Copies of radiological scans and autopsy reports (and other documents) that may be requested by the Sponsor should be de-identified. The Investigator shall obtain all such permissions and authorizations as may be necessary or desirable to allow the collection and use of information protected under federal privacy laws and state privacy laws, including permission/authorization for monitoring and analysis (including re-analysis in combination with results of other studies), for regulatory submission purposes and for applicable reporting (if any) required to be made by Sponsor, its affiliates and their designee.

11.6 STUDY REPORT AND PUBLICATIONS

A final integrated clinical/statistical report will be prepared that is compliant with the ICH Harmonized Tripartite Guideline: Structure and Content of Clinical Study Reports (CPMP/ICH/137/95). The results of this study will be published and/or presented at scientific meetings in a timely manner. The publication policy is described in the contract between the Sponsor and Investigator.

11.7 STUDY FILES AND RETENTION OF RECORDS

Copies of all study documents should be retained by the Investigator until at least two years after the last approval of a marketing application in an ICH region and until there are no pending or contemplated marketing applications in an ICH region or at least two years have elapsed since the formal discontinuation of clinical development of the investigational product, in accordance with 21 CFR 312.62. These documents should be retained for a longer period however, if required by regulatory requirements or by agreement with the Sponsor. It is the responsibility of the Sponsor to inform the Investigator/institution as to when these documents no longer need to be retained. The final database will be archived according to the regulatory requirements.

11.8 CASE REPORT FORMS

Data for this protocol will be captured electronically in an Electronic Data Capture (EDC) system. Designated study personnel will be provided unique user names and passwords. Each study personnel will have specific access within the electronic data collection system based on

their role. The EDC system contains an audit trail associated with each individual's unique password that will document date and time of data entry and revisions. All protocol-specified data is to be entered into the EDC system in a timely manner for review and audit by XBiotech USA, Inc. All data is to be entered such that it will allow accurate interpretation and tabulation. It is the Investigator's responsibility to ensure that all discontinued orders or changes in study or other medications entered into the database correspond to entries in the subject's medical records (i.e. source documents) and to acknowledge accurate completion of the eCRF.

11.9 DRUG ACCOUNTABILITY

A Drug Dispensing Log must be kept current and should contain the following information:

- Initial inventory upon receipt of supplies at the study site
- Identification number of each subject to whom test drug was administered
- Date(s), quantities, lot numbers and calculations for all test drugs administered
- Final inventory (upon completion of the study)

This inventory must be available for inspection by the Clinical Research Associate. The Investigator (or pharmacist, as appropriate) must maintain records of the delivery of the study medication to the study site, the inventory at the site, the usage for each subject, and destruction. The inventory must be available for monitoring, auditing or inspection. A drug dispensing log must be kept current and should contain the following information:

- The subject identification number to whom the drug is dispensed
- The lot number of the drug dispensed
- The date(s) and the quantity of the drug dispensed to the subject

11.10 INSPECTIONS

Investigator sites, the study database and study documentation may be subject to quality assurance audits during the course of the study either by the Sponsor or their appointed representatives. In addition, regulatory bodies at their discretion may conduct inspections. The Investigator shall permit the authorized Sponsor, agents of the Sponsor, and regulatory agency employees to enter and inspect any site where the drug or records pertaining to the drug are held, and to inspect all records relating to an investigation, including subject records. The Sponsor will not, however, copy any source data from the patient's dossier. Completed eCRFs must be made available by the Investigator for review by the Sponsor, agents of the Sponsor, the CRA and the regulatory agencies. To ensure the accuracy of data submitted, it is mandatory that representatives of the Sponsor and of the regulatory agencies have direct access to source documents (e.g. subject medical records, charts, laboratory reports, etc.). Subject confidentiality will be protected at all times.

11.11 ACCESS TO INFORMATION FOR MONITORING

CRAs will establish and maintain regular contact between the Investigator and the Sponsor. CRAs will evaluate the competence of each study center, informing the Sponsor about any problems relating to facilities, technical equipment or medical staff. During the study, CRAs will check that written informed consent has been obtained from all subjects correctly and that data are recorded correctly and completely. CRAs are also entitled to compare entries in eCRFs with corresponding source data and to inform the Investigator of any errors or omissions. CRAs will

also monitor adherence to the protocol at the Investigator site. They will arrange for the supply of investigational product and ensure appropriate storage conditions are maintained. The CRA will make written reports to the Sponsor on each occasion when contact with the Investigator is made, regardless of whether it is by phone or in person. During monitoring visits, entries in the eCRFs will be compared with the original source documents. The Investigator must agree to meet with the CRA at regular intervals and to cooperate in resolving any queries or findings made during the monitoring process.

11.12 STUDY DISCONTINUATION

If the study is prematurely terminated or suspended, the Sponsor will promptly inform the Investigators/institutions and the regulatory authority(ies) of the termination or suspension and the reason(s) for the termination or suspension. The IRB/EC will also be promptly informed and provided with the reason(s) for the termination or suspension by the Sponsor or by the Investigator/institution, as specified by the applicable regulatory requirement(s).

APPENDIX A

Eastern Cooperative Oncology Group (ECOG) Grades	
Grade	ECOG
0	Fully Active, able to carry on all pre-disease performance without restriction.
1	Restricted in physically strenuous activity but ambulatory and able to carry out work of a light or sedentary nature, e.g. , light housework, office work.
2	Ambulatory and capable of all self-care but unable to carry out any work activities. Up and about more than 50% of waking hours.
3	Capable of only limited self care, confined to bed or chair more than 50% of waking hours.
4	Completely disabled. Cannot carry on any self-care. Totally confined to bed or chair.
5	Dead

